Evaluating Immunogenicity and Safety Effect on Combined Immune Effect of EV71 Inactivated Vaccine and HepB、MPSV-A、MR、JE-L : A Multi-center Randomized Controlled Trial

Registered classification: prevention of biological products

Clinical stage: stage IV

Program number: EV71-2017-03

Version date: 05 01 2018

Bidding unit:

China Biotechnology Limited by Share Ltd

Wuhan biological products research institute limited liability company

Research unit:

Shandong Center for Disease Control and Prevention

Hunan Center for Disease Control and Prevention

Shaanxi Center for Disease Control and Prevention

Shanxi Center for Disease Control and Prevention

Background

To prevent and control the epidemic of HFMD and related diseases caused by EV71 infection, the development of EV71 vaccine has been developed in many countries or regions. According to the requirements of drug registration approval, we need to evaluate immunogenicity and safety effect on combined immune effect of EV71 inactivated vaccine and other vaccines (HepB、MPSV-A、MR、JE-L).

Method

Four experimental groups (HepB:3+EV71, MPSV-A:1+EV71, MR +EV71, JE-L+EV71) were included in this clinical trial. In addition to the meningococcal vaccine research group, the other three groups were followed up for the 4 times. The initial blood samples were collected, and the first dose vaccine was inoculated at the same time. EV71 second doses of vaccine were inoculated at 30 day, the blood was collected after 30 days of immunization with second doses. 6 months of safety follow-up was carried out in the whole clinical trial after vaccination. The meningococcal vaccine research group increased 1 follow-up after the second dose of MPSV-A vaccine. The index of immunogenicity and safety effect in four experimental groups need to be evaluated.

Study design and participants

The study was conducted in four provinces (Shandong, Shanxi, Shaanxi and Hunan) of China, which contains Haiyang city, Rushan city, Shimen County, Chen Cang District, Qishan County, Taigu County and Qi County. 6/8 months children were

recruited in this study, individuals were randomly assigned to experimental group and control group. Demographic information (age, sex, height and weight) was made and blood samples were collected for each individual in the same way.

Inclusion Criteria

Inclusion criteria for group I (HepB:3+EV71) were as follows: (1)aged ≥ 6 months; (2)sign the informed consent form; (3)the legal guardian participate in all the planned follow-up and be able to comply with all research procedures; (4)the subjects have completed the basic immunization of 2 needle recombinant hepatitis B vaccine, there is no inoculation history of EV71 vaccine, and there is no history of EV71 infection ; (5)the last vaccination intervals ≥ 14 days ; (6)temperature $\leq 37C^{\circ}$

Inclusion criteria for group II (MPSV-A:1+EV71) were as follows: (1)aged ≥ 6 months; (2)sign the informed consent form; (3)the legal guardian participate in all the planned follow-up and be able to comply with all research procedures; (4)there is no inoculation history of EV71 vaccine, and there is no history of EV71 infection; (5)the last vaccination intervals ≥ 14 days ; (6)temperature $\leq 37C^{\circ}$

Inclusion criteria for group III (MR+EV71) were as follows: (1)aged ≥ 8 months; (2)sign the informed consent form; (3)the legal guardian participate in all the planned follow-up and be able to comply with all research procedures; (4)there is no inoculation history of EV71 vaccine, and there is no history of EV71 infection; (5)the last vaccination intervals ≥ 14 days and the last attenuated live vaccine intervals ≥ 28 days ; (6)temperature $\leq 37C^{\circ}$

Inclusion criteria for group IV (JE-L+EV71) were as follows: (1)aged ≥ 8 months; (2)sign

the informed consent form; (3)the legal guardian participate in all the planned follow-up and be able to comply with all research procedures; (4)there is no inoculation history of EV71 vaccine, and there is no history of EV71 infection; (5)the last vaccination intervals ≥ 14 days and the last attenuated live vaccine intervals ≥ 28 days ; (6)temperature $\leq 37C^{\circ}$

Exclusion Criteria

Exclusion criteria for first needle: (1) the history or family history of anaphylaxis, convulsion, epilepsy, encephalopathy and psychosis; (2) the history of severe inoculation allergies; (3)patients with immunodeficiency and malignant tumors during the treatment period, receiving immunosuppressive therapy (oral steroid) or HIV due to low immunity, or family members have congenital immune disease; (4)Nonspecific immunoglobulin was injected within one month; (5)temperature $> 37.1C^{\circ}$ and infectious diseases; (6)the history of thrombocytopenia or other thrombocytopenia with a definite diagnosis; (7)respiratory disease, acute infection or chronic disease activity period; (8)severe cardiovascular disease (CVD, pulmonary edema, hypertension can not be controlled by drugs to the normal range), liver and kidney disease, and complications of diabetes; (9)infectious, suppurative and allergic dermatosis; (10)other conditions that may affect the evaluation of the trail

Exclusion criteria for follow-up needle: (1)any serious adverse events that have a causal relationship with the inoculation of the upper dose of the vaccine; (2)the abnormality of 4 levels (local, systemic adverse reactions and vital signs) was judged to be related to vaccination; (3)other new

standards of "Exclusion criteria for first needle";(4)other conditions that may affect the evaluation of the trail

Vaccine inoculation and follow-up

Test I (HepB:3+EV71):

Experimental group - 6 month old HepB third dose and EV71 first dose were inoculated at the same time, 7 month old EV71 second dose was inoculated, blood samples from the participants were collected at 8 month old;

Control group 1- 6 month old HepB third dose was inoculated separately, blood samples from the participants were collected after two months;

Control group 2 - 6 month old EV71 first doses was inoculated, 7 month old EV71 second dose was inoculated, blood samples from the participants were collected at 8 month old.

Test II (MPSV-A:1+EV71):

Experimental group - 6 month old MPSV-A first dose and EV71 first dose were inoculated at the same time, 7 month old EV71 second dose was inoculated, 9 month old MPSV-A second dose was inoculated, blood samples from the participants were collected at 10 month old;

Control group 1- 6 month old MPSV-A first dose was inoculated separately, 9 month old MPSV-A second dose was inoculated separately, blood samples from the participants were collected at 10 month old;

Control group 2 - 6 month old EV71 first doses was inoculated, 7 month old EV71 second dose was inoculated, blood samples from the participants were collected

at 10 month old.

Test III (MR+EV71):

Experimental group - 8 month old MR first dose and EV71 first dose were inoculated at the same time, 9 month old EV71 second dose was inoculated, blood samples from the participants were collected at 10 month old.

Control group 1- 8 month old MR first dose was inoculated separately, blood samples from the participants were collected at 10 month old;

Control group 2 - 8 month old EV71 first doses was inoculated, 9 month old EV71 second dose was inoculated, blood samples from the participants were collected at 10 month old.

Test IV (JE-L+EV71):

Experimental group - 8 month old JE-L first dose and EV71 first dose were inoculated at the same time, 9 month old EV71 second dose was inoculated, blood samples from the participants were collected at 10 month old.

Control group 1- 8 month old JE-L first dose was inoculated separately, blood samples from the participants were collected at 10 month old;

Control group 2 - 8 month old EV71 first doses was inoculated, 9 month old EV71 second dose was inoculated, blood samples from the participants were collected at 10 month old.

EV71 vaccine 0.5ml per dose, Wuhan Biological Products Co., Ltd., Wuhan, Hubei Province, China; 10µg HepB 0.5ml per dose, Wuhan Biological Products Co., Ltd., Wuhan, Hubei Province, China; 30ug MPSV-A 0.5ml per dose, Wuhan Biological

Products Co., Ltd., Wuhan, Hubei Province, China; MR 0.5ml per dose, Beijing Biological Products Co., Ltd., Beijing, China; JE-L 0.5ml per dose, Chengdu Biological Products Co., Ltd., Chengdu, Sichuan Province, China

Immunogenicity end point

Detection of serum antibody EV71 vaccine by culture neutralization test, the definition of positive for neutralizing antibody titers of $<1:8$ before inoculation, inoculation after neutralizing antibody titers than $1:8$; or before inoculation neutralizing antibody titer is above $1:8$, the titer of neutralizing antibody after vaccination appeared more than 4 times the growth. Hepatitis B vaccine seroconversion was defined as Anti-HBs $<10\text{mIU/ml}$ before inoculation, Anti-HBs after inoculation was more than 10mIU/ml . Leprosy vaccine using measles rubella immunoglobulin ELISA detection test, measles $>200\text{U/ml}$ positive for rubella $>20\text{U/ml}$ positive or positive before inoculation; after inoculation, antibody positive growth is more than 4 times. Japanese encephalitis vaccine serum samples by using PRNT test before immunization antibody titer after inoculation was less than $1:5$, at $1:10$, or after vaccination antibody titer than before inoculation is no less than 4 times of growth is positive. Meningococcal vaccine samples A meningococcal bactericidal antibody level in serum by micro bactericidal antibody test, the antibody titer after inoculation than before inoculation is no less than 4 times of growth is positive.

Safety assessment

Safety assessment Participants were provided with diary cards to record the

occurrence and severity of solicited local reactions at the injection site (pain, induration, erythema, edema, pruritus) during 7 days after vaccination, solicited systemic reactions (fever, headache, fatigued, cough, myalgia, asthenia, vertigo, diarrhea), and any unsolicited adverse during 29 days after vaccination.

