Active Comparator: Separate inoculation control group Group I : HepB:3 Group II : MPSV-A:1 Group III: MR Group IV: JE-L Inoculation vaccine made by different techniques (EV71 vaccine 0.5ml per dose, Wuhan Biological Products Co., Ltd., Wuhan, Hubei Province, China; 10 μ g HepB 0.5ml per dose, Wuhan Biological Products Co., Ltd., Wuhan, Hubei Province, China; 30ug MPSV-A 0.5ml per dose, Wuhan Biological Products Co., Ltd., Wuhan, Hubei Province, China; MR 0.5ml per dose, Beijing Biological Products Co., Ltd., Beijing, China; JE-L 0.5ml per dose, Chengdu Biological Products Co., Ltd., Chengdu, Sichuan Province, China) were given intramuscularly in the deltoid region to participants.

Active Comparator: EV71 inoculation control group Group I : EV71 Group II : EV71 Group III: EV71 Group IV: EV71 Inoculation vaccine made by different techniques (EV71 vaccine 0.5ml per dose, Wuhan Biological Products Co., Ltd., Wuhan, Hubei Province, China; 10 μ g HepB 0.5ml per dose, Wuhan Biological Products Co., Ltd., Wuhan, Hubei Province, China; 30ug MPSV-A 0.5ml per dose, Wuhan Biological Products Co., Ltd., Wuhan, Hubei Province, China; MR 0.5ml per dose, Beijing Biological Products Co., Ltd., Beijing, China; JE-L 0.5ml per dose, Chengdu Biological Products Co., Ltd., Chengdu, Sichuan Province, China) were given intramuscularly in the deltoid region to participants.

Assigned Interventions

Biological/Vaccine: Inoculation vaccine EV71 vaccine 0.5ml per dose, Wuhan

Biological Products Co., Ltd., Wuhan, Hubei Province, China 10µg HepB 0.5ml per dose, Wuhan Biological Products Co., Ltd., Wuhan, Hubei Province, China 30ug MPSV-A 0.5ml per dose, Wuhan Biological Products Co., Ltd., Wuhan, Hubei Province, China MR 0.5ml per dose, Beijing Biological Products Co., Ltd., Beijing, China JE-L 0.5ml per dose, Chengdu Biological Products Co., Ltd., Chengdu, Sichuan Province, China

Outcome Measures

Primary Outcome Measure:

1. Statistical analysis of immunogenicity 1. Serum antibody positive rate, antibody 4 times growth rate, antibody positive rate (4 times increase) rate and confidence interval, and non-inferiority test of antibody positive rate 2. Antibody titer / concentration distribution before and after immunization.

2. Secondary Outcome Measure:

2. Population characteristics of the subjects 1. Demographic equilibrium and basic statistical indicators 2. the number of entering, completing, falling off, deviating from the scheme and the reasons

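### Does the 10-month blood draw in Test II leave the EV71 and MPSV-A endpoints undefined?

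*Protocol*

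**What the plan says.** The protocol's Method section gives a general timetable: "EV71 second doses of vaccine were inoculated at 30 day, the blood was collected after 30 days of immunization with second doses". The same paragraph treats the meningococcal group separately. It introduces the visit count with "In addition to the meningococcal vaccine research group, the other three groups were followed up for the 4 times" and ends with "The meningococcal vaccine research group increased 1 follow-up after the second dose of MPSV-A vaccine".

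The section on vaccine inoculation and follow-up then sets out each test arm by arm. For Test II:

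- Experimental arm: "6 month old MPSV-A first dose and EV71 first dose were inoculated at the same time". EV71 dose 2 comes at 7 months, and the rest of the entry reads "EV71 second dose was inoculated, 9 month old MPSV-A second dose was inoculated, blood samples from the participants were collected at 10 month old".
- The arm without EV71 (control group 1): MPSV-A at 6 and 9 months, blood at 10 months.
- Control group 2: "6 month old EV71 first doses was inoculated, 7 month old EV71 second dose was inoculated", no MPSV-A, blood at 10 months.

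The endpoint texts are generic about time. Under Immunogenicity end point, the MPSV-A response is defined as "the antibody titer after inoculation than before inoculation is no less than 4 times of growth is positive", and the EV71 response is likewise defined by titres before and after vaccination. The SAP's primary outcome lists "Antibody titer / concentration distribution before and after immunization". None of these names a dose or a sampling day.

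**The concern.** Read alone, the Method sentence promises a sample 30 days after the second doses, and Test II does not deliver that for EV71. The added meningococcal follow-up is mentioned without a blood sample, so the Method section does not say whether it replaces a 30-day draw or comes on top of one.

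The stake is what a primary endpoint means. A 3-month EV71 response could be set beside the 1-month responses of Tests I, III and IV as if they were the same measure. The MPSV-A sample follows a second dose given without EV71, so any interference with the co-administered first dose could have been made up by the time of sampling. The group label, MPSV-A:1+EV71, invites a conclusion about that first dose. In addition, the experimental arm has had two MPSV-A doses by the time its EV71 titre is measured, whereas control group 2 has had none.

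**Working it through.** The inputs are the ages listed in the protocol's section on vaccine inoculation and follow-up. The interval is age at draw minus age at dose, in months, with one month taken as about 30 days.

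**The plan's 30-day figure, in arms that receive EV71**

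- Test I, experimental arm and control 2: 8 - 7 = 1 month.
- Tests III and IV, experimental arm and control 2: 10 - 9 = 1 month.

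The Method figure is reproduced in all of these.

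**Test II**

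| Arm | After EV71 dose 2 | After MPSV-A dose 2 | After MPSV-A dose 1 |
|---|---|---|---|
| Experimental | 10 - 7 = 3 | 10 - 9 = 1 | 10 - 6 = 4 |
| Control 1 | no EV71 | 10 - 9 = 1 | 10 - 6 = 4 |
| Control 2 | 10 - 7 = 3 | no MPSV-A | no MPSV-A |

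For EV71 the 30-day figure is not reproduced: the interval is about 3 x 30 = 90 days. If second doses is taken to mean MPSV-A dose 2, 30 days fits the experimental arm and control 1 but not control 2, whose only second dose is EV71.

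**Balance within each comparison**

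- EV71, experimental arm against control 2: 3 months after dose 2 in both, difference 3 - 3 = 0.
- MPSV-A, experimental arm against control 1: 1 month after dose 2 in both (1 - 1 = 0) and 4 months after dose 1 in both (4 - 4 = 0).

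**Which samples enter the endpoint**

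The Method section places the initial sample at the first dose. The Test II schedule lists one later sample per arm. A before-and-after definition applied to that schedule can use only the initial sample and the 10-month sample. No 8-month draw is listed.

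**Method section against Test II schedule**

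The opening words about the meningococcal group, followed by the other three groups as the subject, read most naturally as an exception. The day-30 and 30-day-blood statements then describe the other three tests, and the paragraph closes by saying how the meningococcal group differs. The arm-level schedule is the more specific text, and it is consistent across all three Test II arms.

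**The case for a change.** The strongest case for a change is that these are primary endpoints, a clarification would cost only words, and no sentence settles the point outright. The Method section does not state the exemption, the added follow-up mentions no blood, and rereading second doses as MPSV-A does not rescue control 2. If MPSV-A dose 2 converts infants who failed to respond to dose 1, a real loss at the co-administered dose would shrink before it is measured.

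Much of this stands as description. The EV71 interval in Test II does differ from the other tests, the endpoint texts do not name the draw, and the MPSV-A result cannot isolate dose 1. It does not show that the plan leads to a wrong result:

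- Neither document says that the Test II EV71 result will be reported as a 30-day response, that EV71 results will be pooled across tests, or that non-inferiority will be claimed for MPSV-A dose 1 alone. The group label identifies the dose given together with EV71; it is not an endpoint definition.
- The response after the two-dose series is a legitimate endpoint. Preferring a dose-1 or 30-day measure is a preference about design.
- Unequal intervening doses come with the three-arm layout. In Tests I, III and IV the experimental arm also receives EV71 dose 2 before the draw, while control 1 receives no EV71.
- The masking effect cannot be sized. The documents give no response rates after either MPSV-A dose, so any figure would rest wholly on assumption and could run from no masking to complete masking.

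**Conclusion.** The concern does not call for a change. The arithmetic behind it is right: in Test II the EV71 response is measured 3 months after dose 2, against 1 month in the other tests, and the MPSV-A response is measured 1 month after dose 2 and 4 months after the co-administered dose 1. The schedule nevertheless fixes a single post-vaccination draw at one age in all three arms, and the interval difference within each comparison is zero. An analyst following it has one sample to use and obtains a sound contrast for each antigen.

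The gap is one of labelling. A competent report would give the interval for Test II EV71, keep it apart from the 1-month results, describe its contrast as EV71 with two MPSV-A doses against EV71 alone, and confine the MPSV-A conclusion to the completed series. Aligning the Method sentence with the Test II schedule would be tidy, but it would alter no sample, visit, dataset or test.

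This rests on two assumptions: the arm-level schedule is complete, so no unlisted earlier draw exists in Test II, and the Method paragraph's separate treatment of the meningococcal group is meant as an exception. The first follows the listed text; the second is the most natural reading, though not an explicit statement.

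### Three of the eight solicited systemic reactions (headache, myalgia, vertigo) cannot be reported by infants of about 6 to 10 months, and no observable substitute is given

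*Protocol*

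**What the plan says.** The Safety assessment section of the protocol gives participants diary cards on which occurrence and severity are recorded. The systemic list is "solicited systemic reactions (fever, headache, fatigued, cough, myalgia, asthenia, vertigo, diarrhea". The same sentence adds "any unsolicited adverse during 29 days after vaccination", and the Method section says that "6 months of safety follow-up was carried out in the whole clinical trial after vaccination".

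The participants are infants. Under Vaccine inoculation and follow-up, the Test I experimental arm starts with "6 month old HepB third dose and EV71 first dose were inoculated at the same time" and the Test II experimental arm with "6 month old MPSV-A first dose and EV71 first dose were inoculated at the same time". Tests III and IV start at 8 months. The latest scheduled doses are at 9 months; in Test II, for example, "9 month old MPSV-A second dose was inoculated".

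The guardian appears in Inclusion Criteria, criterion (3), for all four groups: "the legal guardian participate in all the planned follow-up and be able to comply with all research procedures". Nothing is said about how a guardian should judge a symptom.

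The SAP places safety among the secondary outcomes and plans to tabulate adverse-reaction symptoms by severity. It defines none of the symptom terms.

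**The concern.** A solicited list is useful when the person filling in the card can tell whether each item occurred. Headache, myalgia and vertigo do not meet that condition before a child can speak. A guardian who sees a crying or listless infant has no stated basis for ticking, or grading, any of the three. Entries will tend to be near zero or arbitrary in every arm. Without a shared definition they may also differ between the four provinces.

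Fatigued and asthenia raise a smaller problem. They are close to synonyms and neither is defined, so one drowsy infant could be entered under either term, or under both.

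The list also leaves out signs that a guardian can see: irritability or abnormal crying, reduced feeding and vomiting.

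What is at stake is how the safety tables are read. The trial's title names safety as an aim of the combined-vaccination evaluation. A reader who finds low and similar rates of headache, myalgia and vertigo in the combined and separate arms could take them as reassurance, when those items could not have shown a difference.

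**Working it through.** The plan gives no figure to reproduce here. The check is a count of the list, a derivation of age from the schedule, and a search of both documents for definitions.

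**Step 1. Classify the eight systemic items** (protocol, Safety assessment).

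- Subjective, need the patient's own report: headache, myalgia, vertigo. 3/8 = 37.5%.
- Overlapping and undefined: fatigued, asthenia. 2/8 = 25%.
- Directly observable: fever, cough, diarrhea. 3/8 = 37.5%.

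**Step 2. Age at each scheduled vaccination** (protocol, Vaccine inoculation and follow-up). Entries are months of age; one entry is one arm-level vaccination occasion.

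| Test | Experimental | Control 1 | Control 2 | Occasions |
|---|---|---|---|---|
| I | 6, 7 | 6 | 6, 7 | 2 + 1 + 2 = 5 |
| II | 6, 7, 9 | 6, 9 | 6, 7 | 3 + 2 + 2 = 7 |
| III | 8, 9 | 8 | 8, 9 | 2 + 1 + 2 = 5 |
| IV | 8, 9 | 8 | 8, 9 | 2 + 1 + 2 = 5 |

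Total: 5 + 7 + 5 + 5 = 22. By age: 6 occasions at 6 months, 4 at 7, 6 at 8 and 6 at 9. All 22 lie between 6 and 9 months. The two vaccines are given together on four occasions, the first visit of each experimental arm, at 6, 6, 8 and 8 months.

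**Step 3. Age when the diaries close.** The sentence on systemic reactions can be read as a 7-day or a 29-day window, so both are shown. With a month of 365.25/12 = 30.4 days, 7 days is 7/30.4 = 0.23 month and 29 days is 29/30.4 = 0.95 month.

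- Co-administration in Tests I and II: 6 + 0.23 = 6.23 to 6 + 0.95 = 6.95 months.
- Co-administration in Tests III and IV: 8 + 0.23 = 8.23 to 8 + 0.95 = 8.95 months.
- Latest dose: 9 + 0.95 = 9.95, about 10 months.

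**Step 4. Definitions or proxies.** Neither document gives an observable sign for headache, myalgia or vertigo, or says how fatigued differs from asthenia. The protocol's exclusion criteria for follow-up doses refer to a level-4 abnormality but do not set out the grading scale. The SAP's safety outcome repeats the symptom-by-severity structure without definitions.

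**Step 5. Use of the data.** Safety is a secondary outcome. The SAP's non-inferiority test and t test concern antibody results; no test of safety data is planned.

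**The case against.** The strongest objection is that the diary card is not in the documents. Item wording, guardian instructions and grading would normally sit there, so a brief protocol that omits definitions does not prove that data collection lacked them. This stands as a limit on certainty. It does not remove the problem, because neither document says that such definitions exist, and the list as written does not suit the age group.

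Second, the impact is small. The same list applies to every arm, and observable reactions, unsolicited events, serious adverse events and the 6-month follow-up all remain. This is accepted. The backstop is only partial, however: signs that are not solicited enter the data only if someone volunteers them.

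Third, the protocol's English is loose, and fatigued and asthenia may be one card item rendered twice. That cannot be settled from the text, so this part of the point carries less weight than the three subjective terms.

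Fourth, reduced feeding and vomiting are not specific proxies for headache, myalgia or vertigo. That is true. The proposal replaces items that cannot be assessed with ones that can; it does not claim that they measure the same thing.

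Fifth, local pain and pruritus are also subjective. They are, so the count of 3 of 8, which covers systemic items only, is conservative.

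Finally, the protocol is written largely in the past tense, so cards may already have been used. In that case only the reporting change is available.

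**Conclusion.** The point holds. Three of eight solicited systemic items (37.5%) cannot be reported at the ages scheduled, and two more (25%) overlap without a definition. Similar low rates for headache, myalgia and vertigo should not be read as evidence that co-administration is free of these effects.

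This is a worthwhile, inexpensive correction to a secondary, descriptive outcome. It does not affect the primary immunogenicity analysis. The documents give no reaction rates, so the amount of under-recording cannot be estimated.

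The conclusion rests on three assumptions: that children are vaccinated at the scheduled ages, since the inclusion criteria set only minimum ages; that guardians complete the cards, which is likely but not stated; and that the card carries no observable definitions missing from the protocol.

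**What to change.** 1. In the protocol's Safety assessment section and on the diary card, replace headache, myalgia and vertigo with signs that a guardian can observe: irritability or abnormal crying, reduced feeding, and vomiting.
2. Merge fatigued and asthenia into one defined item, drowsiness or reduced activity.
3. Keep fever, cough and diarrhea.
4. Use the revised list in the SAP's symptom-by-severity tables.

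If the card already carries observable proxies, state them in the protocol. If cards have already been used, report headache, myalgia and vertigo as not reliably assessable at this age, and not as evidence of no difference between arms.

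The cost is a revised card and revised wording in the protocol and SAP tables, with no added visits, blood draws or procedures. The drawback is less comparability with data collected on the present list. If only the reporting caveat applies, it costs one sentence in the safety report.
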